## REAGIR II

Patients presenting to Aravind Eye Hospitals – Madurai (in India) or to the Federal University of São Paulo in Brazil (UNIFESP) with smear-positive and/or culture positive typical (i.e. non-*Nocardia* or *Mycobacteria*) bacterial corneal ulcers and moderate to severe vision loss, defined as Snellen visual acuity of 20/40 or worse, will be eligible for inclusion. Those who agree to participate will be randomised to one of two treatment groups:

- Group 6, RB-PDT Plus Early Steroids: topical 0.5% moxifloxacin plus topical difluprednate 0.05%/prednisolone acetate 1% plus RB-PDT
- Group 7, Sham RB-PDT Plus Early Steroids: topical 0.5% moxifloxacin plus topical difluprednate 0.05%/prednisolone acetate 1% plus sham RB-PDT

We hypothesize that study participants treated with topical antibiotics plus adjunctive RB-PDT will have better best spectacle corrected visual acuity at 6 months compared to those treated with antibiotics alone. The patient, physicians, microbiologist and refractionist performing the best spectacle-corrected visual acuity (BSCVA) assessment will be masked to the treatment group. Due to the nature of the intervention, the surgeon and technician performing cross-linking will not be masked.

### 4.2 SCIENTIFIC RATIONALE FOR STUDY DESIGN

Randomized control trials are known to be the least biased form of evidence; we have chosen to do a randomized control trial with placebo and sham controls to introduce as little bias as possible. Sham cross-linking and placebo with study drug vehicle are included to maintain masking of the study participant and treating physician. No group is receiving less than the standard of care, which is topical antibiotic or antimicrobial treatment.

### 4.3 JUSTIFICATION FOR DOSE

Route of administration and dosage of study medications are consistent with standard practice. For SCUT II, topical placebo will be administered in the same way as topical difluprednate to mask the patient, physician, and study staff. The topical placebo solution will have the same clear appearance as difluprednate to maintain masking.

### 4.4 END OF STUDY DEFINITION

A participant is considered to have completed the study if he or she has completed all phases of the study including the final 12-month visit, as shown in the Schedule of Activities (SoA), **Section 1.3**.

## 5 STUDY POPULATION

### 5.1 INCLUSION CRITERIA

In order to be eligible to participate, an individual must meet all of the following criteria:

#### SCUT II and REAGIR II:

- Corneal ulcer that is smear positive and/or culture positive (within 24 hours) for typical bacteria (i.e. non-*Nocardia* or Myobacteria)
- Moderate to severe vision loss, defined as Snellen visual acuity of 20/40 (6/12) or worse
- Corneal thickness  $\geq 350 \mu\text{m}$ , as measured on AS-OCT
- Age over 18 years
- Basic understanding of the study as determined by the physician
- Commitment to return for follow up visits

#### REAGIR:

- Presence of smear or culture positive fungal or acanthamoeba ulcer; smear or culture negative ulcer; or any atypical bacteria (such as *Nocardia*)
- Moderate to severe vision loss, defined as Snellen visual acuity of 20/40 (6/12) or worse
- Corneal thickness  $\geq 350 \mu\text{m}$ , as measured on AS-OCT
- Age over 18 years
- Basic understanding of the study as determined by the physician
- Commitment to return for follow up visits

### 5.2 EXCLUSION CRITERIA

An individual who meets any of the following criteria will be excluded from participation in this study:

- Evidence of concomitant infection on exam, gram stain, or confocal microscopy (i.e. herpes, both bacteria and acanthamoeba on gram stain)
- Impending or frank perforation at recruitment
- Involvement of sclera at presentation
- Presence of desmetocele at recruitment
- Non-infectious or autoimmune keratitis
- History of corneal transplantation
- History of intraocular surgery within the last three months\*
- Pinhole visual acuity worse than 20/200 in the unaffected eye
- Participants who are decisionally and/or cognitively impaired

\*Recent intraocular surgery is an exclusion to avoid ulcers related to the surgery itself (e.g.: wound infection). Three months post-surgery is generally acceptable, although the ophthalmologist can judge whether, in their opinion, the ulcer is related to the surgery. For example, one month after an uncomplicated cataract surgery might be considered acceptable.

### 5.3 LIFESTYLE CONSIDERATIONS

Patients at some Aravind Eye Hospital enrollment centers will be admitted to the inpatient setting for the first 3 days of the study.

## 5.4 SCREEN FAILURES

Screen failures are defined as participants who consent to participate in the clinical trial but are not subsequently randomly assigned to the study intervention or entered in the study. A minimal set of screen failure information is required to ensure transparent reporting of screen failure participants, to meet the Consolidated Standards of Reporting Trials (CONSORT) publishing requirements and to respond to queries from regulatory authorities. Minimal information includes demography, screen failure details, eligibility criteria, and any serious adverse event (SAE). In this study, all patients who are enrolled will be randomized and included in the primary analysis, regardless of whether or not they actually receive the assigned intervention.

## 5.5 STRATEGIES FOR RECRUITMENT AND RETENTION

Patients presenting to recruitment sites with smear-positive typical bacterial corneal ulcers, smear or culture positive fungal or acanthamoeba ulcers, or smear or culture negative ulcers with moderate to severe vision loss will be approached for possible inclusion in the study. For eligible patients, the study will be explained in the local language (Tamil at the Aravind Eye Clinics, English or Spanish at UCSF and University of Miami, and Portuguese at UNIFESP) in addition to the risks and benefits of participating in the study. Patients at some Aravind sites will be admitted to the hospital for the first 3 days of the study, ensuring minimal loss to follow-up through day 3. Patients will schedule their follow up visits with the study coordinator while they are in inpatient care. The study coordinator will give the patient written documentation of their upcoming visits, and will follow-up with a phone call as their appointments approach. Previous studies with Aravind and UCSF, including the original Steroids for Corneal Ulcers Trial, the Mycotic Ulcer Treatment Trials I & II, and the small cross-linking for bacterial keratitis feasibility assessment study we performed, have had high retention and leave us confident that this study will have high retention as well.

# 6 STUDY INTERVENTION

## 6.1 STUDY INTERVENTION(S) ADMINISTRATION

### 6.1.1 STUDY INTERVENTION DESCRIPTION

#### SCUT II: Corneal Cross-Linking with Riboflavin

Participants in Groups 1, 2, & 3 will begin study drug (topical difluprednate 0.05% or placebo) within 24 hours after enrollment.

Participants in Group 3 will receive UVX (modified Dresden protocol), and Groups 1 & 2 will receive sham UVX within 48 hours of enrollment. All participants will receive a 30-minute loading dose of topical 0.1% riboflavin and 20% dextran T500 drops every 2 minutes. For Group 3, this will be followed by exposure to UV-A light at a wavelength of 365 nm with an irradiance of 3 mW/cm^2 for 30 minutes for a total dose of 5.4 J/cm^2 (UV lamp: PESCHKE Meditrade GmbH, Hueneberg, Switzerland for India; Avedro KXL System, Waltham, MA, USA for USA). During irradiation patients will continue to receive topical riboflavin at 5-minute intervals. For Groups 1 & 2, sham UVX simulates this experience however the light will be shined adjacent to the patient, careful to avoid exposure to the cornea. In place of riboflavin we will use either saline drops or saline drops dyed with fluorescein.

***Moxifloxacin 0.5%***

Topical moxifloxacin 0.5% is a fluoroquinolone antibiotic that is used to treat bacterial infections. This is standard therapy for bacterial keratitis. Immediately after UVX/sham UVX and repeat culture, all participants will receive topical moxifloxacin drops every 1 hour for 2 days, and then every 2 hours while awake until resolution of the epithelial defect.

***Difluprednate 0.05%***

Difluprednate 0.05% is a corticosteroid used to reduce inflammation in the eye. Participants in Groups 2 & 3 will receive one drop of 0.05% difluprednate four times daily beginning 24 hours after the initiation of antibiotics for 1 week, decreased by 1 drop weekly for a total of 4 weeks of steroid therapy.

***Placebo***

Participants randomized to Group 1 will receive topical placebo in place of topical difluprednate. The placebo will be the vehicle used in difluprednate. Group 1 will receive the topical placebo on the same medication schedule described above for difluprednate.

***REAGIR: Corneal Cross-Linking with Rose Bengal***

Participants in Groups 4 and 5 will begin topical antimicrobial at enrollment.

Participants in Group 5 will receive RB-PDT and Group 4 will receive sham RB-PDT within 48 hours of randomization. Group 5 participants will receive a 30-minute loading dose of topical Rose Bengal (0.1% RB in 0.9% sodium chloride) which will be applied in 3-minute intervals to the de-epithelialized cornea. This will be followed by irradiation with a 6mW/cm^2 custom-made green LED source for 15 minutes (5.4J/cm^2). Participants in Group 4 will undergo a sham procedure using topical balanced salt solution and pen light covered with a green filter. Participants in both groups will undergo repeat cornea cultures within 24 hours after the procedure.

***Rose Bengal 0.1%***

Rose Bengal (RB) is one of the most commonly used dyes in the diagnosis of ocular surface disease. Rose Bengal is an effective photosensitizer, readily converting triplet oxygen (O2) to produce high singlet oxygen (O2) yields with exposure to green light. Although RB dye penetration is to approximately 100µm into the stroma, subsequent free radical formation occurs up to 1/3 of the corneal stromal depth. The ability of RB to continue free radical formation is self-limited after photo-irradiation has ceased.

***Chlorhexidine gluconate 0.02% or polyhexamethylene biguanide 0.02%***

Topical biguanides such as chlorhexidine gluconate 0.02% or PHMB 0.02% are thought to be the most effective available medical therapy for acanthamoeba. Participants in Groups 4 and 5 with acanthamoeba ulcers will receive topical chlorhexidine drops every 1 hour for 2 days, and then every 2 hours while awake, tapering at the clinician's discretion.

***Moxifloxacin 0.5%***

At enrollment, participants with smear/culture negative ulcers will receive topical moxifloxacin drops every 1 hour for 2 days, and then every 2 hours while awake, tapering at the clinician's discretion.

***Natamycin 5%***

Topical natamycin, a polyene, is the only antifungal agent approved by the Food and Drug Administration (FDA) for treatment of fungal keratitis. Participants in Groups 4 and 5 with fungal ulcers

will receive topical natamycin every 1 hour for 2 days, and then every 2 hours while awake, tapering at the clinician's discretion.

#### Amphotericin B 0.15%

In Brazil, participants in Groups 4 and 5 with fungal ulcers will receive topical amphotericin B 0.15% every 1 hour for 2 days, then every 2 hours while awake, tapering at the clinician's discretion.

#### **REAGIR II: Corneal Cross-Linking with Rose Bengal**

Participants in Groups 6 and 7 will begin topical difluprednate 0.05% within 24 hours after enrollment.

RB-PDT/sham RB-PDT will occur within 48 hours of randomization. For Group 6, Rose Bengal (0.1% RB in 0.9% sodium chloride) will be applied in 3-minute intervals to the de-epithelialized cornea for 30 minutes followed by irradiation with a 6mW/cm^2 custom-made green LED source for 15 minutes (5.4J/cm^2). Participants in Group 7 will undergo a sham procedure using topical balanced salt solution and pen light covered with a green filter. Participants in both groups will undergo repeat cornea cultures within 24 hours after the procedure.

#### *Rose Bengal 0.1%*

Rose Bengal (RB) is one of the most commonly used dyes in the diagnosis of ocular surface disease. Rose Bengal is an effective photosensitizer, readily converting triplet oxygen (O2) to produce high singlet oxygen (O2) yields with exposure to green light. Although RB dye penetration is to approximately 100µm into the stroma, subsequent free radical formation occurs up to 1/3 of the corneal stromal depth. The ability of RB to continue free radical formation is self-limited after photo-irradiation has ceased.

#### *Moxifloxacin 0.5%*

Topical moxifloxacin 0.5% is a fluoroquinolone antibiotic that is used to treat bacterial infections. This is standard therapy for bacterial keratitis. Immediately after UVX/sham UVX and repeat culture, all participants will receive topical moxifloxacin drops every 1 hour for 2 days, and then every 2 hours while awake until resolution of the epithelial defect.

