## REAGIR II

With SCUT II closed to enrollment, participants with typical bacterial corneal ulcers will be randomized to one of two possible treatment arms:

- Group 6, RB-PDT Plus Early Steroids: topical 0.5% moxifloxacin plus topical difluprednate 0.05%/prednisolone acetate 1% plus RB-PDT
- Group 7, Sham RB-PDT Plus Early Steroids: topical 0.5% moxifloxacin plus topical difluprednate 0.05%/prednisolone acetate 1% plus sham RB-PDT

Participants in Groups 6 & 7 will begin topical difluprednate 0.05% (India) or prednisolone acetate 1% (Brazil) within 24 hours after enrollment. The affected eye will receive one drop of 0.05% difluprednate/prednisolone acetate 1% four times daily beginning 24 hours after the initiation of antibiotics for 1 week, decreased by 1 drop weekly for a total of 4 weeks of steroid therapy.

RB-PDT/sham RB-PDT will occur within 48 hours of randomization. For Group 6, Rose Bengal (0.1% RB in 0.9% sodium chloride) will be applied in 3-minute intervals to the de-epithelialized cornea for 30 minutes followed by irradiation with a 6mW/cm^2 custom-made green LED source for 15 minutes (5.4J/cm^2). They will undergo repeat cornea cultures within 24

hours after the procedure. Participants in Group 7 will undergo a sham procedure using topical balanced salt solution and pen light covered with a green filter.

[figure not shown]

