#### *Difluprednate 0.05%/Prednisolone acetate 1%*

Difluprednate 0.05% and Prednisolone acetate 1% are both corticosteroids used to reduce inflammation in the eye. Participants in Groups 2 & 3 will receive one drop of 0.05% difluprednate (India) or prednisolone acetate 1% (Brazil) four times daily beginning 24 hours after the initiation of antibiotics for 1 week, decreased by 1 drop weekly for a total of 4 weeks of steroid therapy.

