**REAGIR II: Dosing schedule for medications**

	Group 6: RB-PDT + Early Steroids		Group 7: Sham RB-PDT + Early Steroids	
	Dose	Duration	Dose	Duration
Moxifloxacin 0.5%	Q 1 hours x 2 days, then Q 2 hours while awake	Until resolution of epithelial defect	Q 1 hours x 2 days, then Q 2 hours while awake	Until resolution of epithelial defect
Steroid (Difluprednate 0.05% or Prednisolone Acetate 1%)	QID	Starting at 24 hours after initiation of antibiotics for 1 week, then decreasing by 1 drop weekly for a total of 4 weeks of steroid therapy	QID	Starting at 24 hours after initiation of antibiotics for 1 week, then decreasing by 1 drop weekly for a total of 4 weeks of steroid therapy
Rose Bengal 0.1% RB in 0.9% sodium chloride	Q2 min	60 minutes		
Homatropine	TID	3 days	TID	3 days

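### REAGIR II's start rules for steroid and moxifloxacin are inconsistent: read as meaning RB-PDT, they cannot all be met by a participant not already on antibiotic

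*Protocol*

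**What the plan says.** All references are to the Protocol, REAGIR II text, unless stated.

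- **Enrollment limit on steroid.** Synopsis, Description of Study Intervention: "Participants in Groups 6 & 7 will begin topical difluprednate 0.05% (India) or prednisolone acetate 1% (Brazil) within 24 hours after enrollment". Section 6.1.1: "Participants in Groups 6 and 7 will begin topical difluprednate 0.05% within 24 hours after enrollment".
- **Antibiotic clock for steroid.** The next sentence of the Synopsis has the drops "four times daily beginning 24 hours after the initiation of antibiotics for 1 week". The steroid paragraph of 6.1.1 agrees ("prednisolone acetate 1% (Brazil) four times daily beginning 24 hours after the initiation of antibiotics for 1 week"), although it assigns the treatment to Groups 2 & 3, which are SCUT II groups. The 6.1.2 dosing table for Groups 6 and 7 has "Starting at 24 hours after initiation of antibiotics for 1 week".
- **Antibiotic start.** The moxifloxacin paragraph of 6.1.1: "Immediately after UVX/sham UVX and repeat culture, all participants will receive topical moxifloxacin drops every 1 hour for 2 days". The same sentence stands in the SCUT II part of 6.1.1.
- **Procedure.** "RB-PDT/sham RB-PDT will occur within 48 hours of randomization". The Schedule of Activities (1.3) puts cross-linking at Day 2.
- **Repeat culture.** At the time of cross-linking for Groups 6 and 7 (1.3 footnote), but up to 24 hours after the procedure in the Synopsis and 6.1.1.

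Two other places bear on the intended antibiotic start, and they point in opposite directions. REAGIR (Groups 4 and 5) starts its antimicrobial at enrollment (6.1.1). Section 9.4.2, Microbiological cure, says all participants are re-cultured at Day 2 before antibiotics start, in text otherwise built around Groups 1 to 3.

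**The concern.** A site coordinator treating an active bacterial ulcer needs one answer to two questions: when does moxifloxacin start, and when does the steroid start? The two steroid rules agree only if antibiotic is on board by enrollment. The only sentence in REAGIR II's own intervention text that times the first moxifloxacin dose puts it after the procedure. Sites could resolve this differently.

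The order and spacing of the two drugs matter clinically. The reassurance in 2.3.1 that steroid did not potentiate infection comes from SCUT, where steroid followed 48 hours of moxifloxacin (2.2). The early-steroid rationale in 2.2 is also timed from antibiotics, not from enrollment. The stakes are therefore consistent delivery and a clear safety rule. The validity of the treatment contrast is not at issue.

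**Working it through.** The documents give no figure for this, so the check is whether the rules can hold together.

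**Inputs (hours from enrollment)**
- Enrollment and randomization both at 0 (assumption; this favors the plan).
- P = start of procedure, 0 to 48 (6.1.1).
- Procedure length: 30 min dye + 15 min light = 0.75 h (6.1.1).
- c = delay from end of procedure to repeat culture: 0 if taken at the procedure (1.3 footnote), up to 24 (Synopsis, 6.1.1).
- A = antibiotic start; S = steroid start.

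**Rules**
1. S ≤ 24 (enrollment limit).
2. S = A + 24 (antibiotic clock).
3. A = P + 0.75 + c (moxifloxacin paragraph, read as RB-PDT/sham RB-PDT).

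Rules 1 and 2 give A ≤ 0. Rule 3 gives A ≥ 0.75 even with P = 0 and c = 0. The three cannot hold together.

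**Size of the conflict**
- If the antibiotic clock is kept: S = P + 24.75 + c, which overshoots the limit by P + 0.75 + c.
- If the enrollment limit is kept: antibiotic leads steroid by at most 24 − A = 23.25 − P − c.

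| P | c | A | S on antibiotic clock | Overshoot | Greatest antibiotic lead if limit kept |
|---|---|---|---|---|---|
| 0 | 0 | 0.75 | 24.75 | 0.75 | 23.25 |
| 12 | 0 | 12.75 | 36.75 | 12.75 | 11.25 |
| 24 | 0 | 24.75 | 48.75 | 24.75 | −0.75 |
| 48 | 0 | 48.75 | 72.75 | 48.75 | −24.75 |
| 48 | 24 | 72.75 | 96.75 | 72.75 | −48.75 |

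A negative lead means steroid before antibiotic. With the procedure on Day 2, P is about 24 if enrollment is on Day 1, where the Schedule of Activities appears to mark consent, and about 48 if it is on Day 0. Which clock sites use is not stated, so the table covers both.

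**Two checks on the source of the conflict**
- Without rule 3, rules 1 and 2 can both be met. The latest antibiotic start is A = 0, giving S = 24.
- If antibiotic began before enrollment and that counts as initiation, both steroid clocks can be met: A = −12 gives S = 12. If it began more than 24 h before, A + 24 falls before enrollment, and the rule works only if read as at least 24 hours.

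**The case against.** **The conflict needs a substitution.** The moxifloxacin sentence names UVX, which Groups 6 and 7 never receive, and is plainly copied from SCUT II. This stands, and the conclusion is conditional on it. Without the substitution, though, REAGIR II's intervention text has no stated time for the first antibiotic dose, which also needs correcting.

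**Not everyone is affected.** The steroid is timed from the start of antibiotics, and the plan expects some participants with prior topical antimicrobial therapy, for whom it plans a subgroup analysis. For them both clocks may be met. This stands: a reader might infer that all 60 planned participants are caught, but the documents do not support that, and they do not give the share already on treatment.

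**Steroid-first dosing is unlikely.** A reader might take the negative leads in the table to mean that the plan directs steroid before antibiotic. It does not. The antibiotic-first rule appears three times, and giving steroid first would mean disregarding it. The likelier outcome is a missed 24-hour limit. The masked physician may also change therapy (6.5.1).

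**Other documents may settle it.** The Manual of Operations and the REAGIR II SAP named in 9.4.1 were not supplied and may contain a timeline. That is possible, but the Protocol is operative dosing text and should agree with them.

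**An enrollment start is not a free correction.** It would contradict 9.4.2 as worded and would change what the Day 2 culture endpoint measures. REAGIR already shows the difficulty: its antimicrobial starts at enrollment, while its SAP (6.2) has the Day 2 culture taken before antibiotics. This stands, so the choice belongs to the sponsor.

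**Conclusion.** This is an internal inconsistency in operative dosing text, and it should be corrected. If the moxifloxacin sentence is read as RB-PDT/sham RB-PDT, a participant not already on antibiotic cannot meet all the start rules. On the antibiotic clock, with culture at the procedure, the 24-hour limit is missed by 0.75 h to 48.75 h. A culture 24 h after a procedure at 48 h raises the overshoot to 72.75 h. These figures assume that enrollment and randomization coincide.

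The same rules apply to both arms, so a reader should not infer bias in the RB-PDT comparison. SCUT II carries the same pair of steroid rules, but the Synopsis says it is closed to enrollment, so the correction is needed for REAGIR II.

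**What to change.** 1. Delete the 24-hours-from-enrollment limit in the Synopsis and in 6.1.1.
2. Keep one steroid clock, worded alike in the Synopsis, the 6.1.1 steroid paragraph and the 6.1.2 table: 24 hours after the first moxifloxacin dose, and never before it.
3. In the REAGIR II moxifloxacin paragraph, replace the UVX reference with an explicit start. The sponsor chooses one:
   - **After RB-PDT/sham RB-PDT and culture.** This agrees with 9.4.2. Steroid then starts 24.75 h to 72.75 h after enrollment with culture at the procedure, or up to 96.75 h if culture may follow by 24 h. The wait for study antibiotic needs a justification, given the standard-of-care statement in 4.2.
   - **At enrollment, as in REAGIR.** Steroid then starts at 24 h. Section 9.4.2 must also be amended to describe the REAGIR II Day 2 culture as taken on treatment.
4. Correct Groups 2 & 3 to Groups 6 & 7 in the 6.1.1 steroid paragraph, and give one repeat-culture time in the Synopsis, 1.3 and 6.1.1.

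Recording the times of the first moxifloxacin and steroid doses in the medication logs of 6.4 would let adherence be checked.

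The cost is wording edits in one IRB-reviewed amendment, with no added visits or participants. The enrollment option has one further cost: the Day 2 culture no longer measures cure before antibiotic.
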